#### **14.2.2 Secondary outcomes**

Secondary outcomes will be analysed for the intention to treat analysis population. Binary outcomes will be analysed using logistic regression with covariates of minimisation factors. The treatment difference will be reported as an OR with corresponding 95% confidence interval. Continuous secondary outcomes such as questionnaires and patient-reported outcome measures (PROMs) will be analysed analogously to the primary outcome using linear regression (95% confidence intervals will not be bootstrapped). Length of hospital stay will be log-transformed analysed using linear regression: summaries on mean fold difference and absolute difference will be presented.

For safety outcomes and adverse events, the following summaries will be presented: the number and percentages of patients reporting SAEs in each arm. In addition, the number of participants requiring further interventions or revisions will be summarised descriptively.

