**Table 3: Internal Pilot Progression criteria**

| Criterion   | Red
(Stop)
(% complete)                 | Amber
(Modify)
(% complete)                | Green
(Go)
(% complete)               |
|---|---|--|---|
| Participant recruitment (number of open centres achieving their individual target recruitment rate of average 2 participants per month) | <60%  | 60-99%   | 100%  |
| Data completeness for primary outcome (number of expected data points recorded for those randomised)                                    | <90%  | 90-99%   | 100%  |
| Return rate for 90-day questionnaire (EQ-5D-5L, Barthel Index & PRO-diGI gastrointestinal recovery measure)                             | <70%  | 70-99%   | 100%  |
| Intervention delivery (nutritional supplementation to have started within 48 hours)   | <70% in intervention arm; >30% in control arm | 70-99% in intervention arm; 1-30% in control arm | 100% in intervention arm; 0% in control arm |
| Cross over rates between arms   | >10%  | ≤10%   | 0%  |

The following actions will be taken:

- If all criteria are **GREEN (Go)**: progress to main trial; following the pilot phase we would still review trial processes to assess whether any changes could/need to be implemented to improve the trial.

- If any of the criteria are **AMBER (Modify)**: review the trial processes to identify implementable changes. This may include recruiting additional centres and/or retraining centres in trial pathways and procedures. We would discuss with the TSC and funder about the need for a second internal pilot phase to verify resolution of issues, then if progress is satisfactory continue to the main trial.
- If any of the criteria are **RED (Stop)**: abandon the trial if the TSC and Funder feel this the appropriate course of action.

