## TONIC: Protocol

---

- Quality of recovery (QoR-15), to measure quality of recovery after surgery and analgesia, participant completed at discharge, 30 and 90 days[42] post-operation.
- Length of post-operative hospital stay from operation to day of discharge (in nights following operation), collected through hospital records.
- Unplanned hospital readmission at 30 and 90 days following discharge up to 90 days post-operation, collected through hospital records.
- Discharge destination (usual residence, residential, or nursing home), collected through hospital records.
- EuroQol-5D-5L[43] (EQ-5D-5L) Health status questionnaire used to derive quality adjusted life years (QALYs), quality of life, and is used in the cost effectiveness analysis, participant completed, at discharge, 30, and 90 days post-operation.
- Patient reported outcome measure of gastrointestinal recovery (PRO-diGI) at discharge, 30, and 90 days post-operation. Includes domains related to pain, nausea, and psychological wellbeing [44].
- Assessment of patient treatment satisfaction using a 0-100 visual analogue scale, patient completed at 30 and 90 days post-operation.
- Use and duration of PN, and total calories administered post-operatively, will be recorded for each arm at discharge.
- Use of other nutritional interventions (oral nutritional supplements) prior to discharge, will also be recorded for each arm.
- Process metrics: time from randomisation to line insertion, and time from operation to starting PN in hours.

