### Baseline (Pre-randomisation)

Once informed consent has been obtained, patients will have key demographic data recorded. The research team will enter the data items needed to determine the Nutrition Risk Screening (NRS-2002) score on to the online EDC system, which will then calculate the score. Data collected as part of routine care includes the MUST, medical history, and the NELA mortality risk score. The patient will also complete an EQ-5D-5L questionnaire. The participant is to be guided to complete the questions on the EQ-5D-5L based on their health and wellbeing prior to the start of the episode that requires surgery. If the participant is not able to complete this then EQ-5D-5L will not be recorded.

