## 14. STATISTICAL CONSIDERATIONS

### 14.1 Sample size

The CCI uses a combination of frequency and weighting to score complications along the CDC framework[36]. Previous literature has demonstrated the standard deviation of this measure to be ~27 for this population[18]. Perinel et al demonstrated an 8-point difference in CCI following early TPN in the elective setting, which corresponded to a 12% reduction in grade III-V complications[43]. Based on the increased acuity and complexity of this patient group, we believe a 6 point reduction in CCI to be a feasible and relevant effect size. A 6-point difference is equivalent to downgrading a class III complication to a class II complication[29]. Allowing for up to 5% attrition, 90% power, 5% two-sided significance threshold, a sample size of 449 participants in each arm is needed (total 898).

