### 14.2.1 Primary outcome(s)

The Comprehensive Complication Index ranges from 0 (no complications) to 100 (death). Previous studies suggest a median CCI score of 21 (IQR 0-29)[8]. Data required to calculate this are all recorded complications, associated with a CDC. Full details of the CCI scoring will be given in the Statistical Analysis Plan (SAP).

The primary analysis will be conducted using linear regression with bootstrapped confidence intervals to account for the non-normal distribution, with covariates comprising randomised arm, site, plus minimisation factors. The treatment difference will be reported as a mean difference with 95% confidence interval. The p-value relating to the intervention group parameter as generated by the model will be presented. The primary analyses will be intention to treat.

As some treatment withdrawal or switchover is expected, the primary outcome will also be analysed using a CACE analysis, in order to estimate the maximal achievable benefit of nutritional supplementation if taken as planned. Further details including per-protocol definition of treatment adherence will be documented in the SAP.

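### The EQ-5D-5L regressions in section 14.2.2 leave out the baseline EQ-5D-5L score that the trial already collects

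*Protocol*

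**What the plan says.** Section 14.2.2 gives the model for questionnaires: "Continuous secondary outcomes such as questionnaires and patient-reported outcome measures (PROMs) will be analysed analogously to the primary outcome using linear regression", with the one stated difference that confidence intervals are not bootstrapped. Section 14.2.1 describes the model being copied as linear regression "with covariates comprising randomised arm, site, plus minimisation factors". The general rule after Table 15 in section 14.2 likewise names only the minimisation variables for adjustment. None of these places lists a baseline outcome score.

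The baseline score exists. Section 9, under Baseline (Pre-randomisation), says: "The patient will also complete an EQ-5D-5L questionnaire". Participants are to answer for their health before the episode that led to surgery, and the score is not recorded if they cannot complete it. Section 8.2.2.1 then schedules EQ-5D-5L as "participant completed, at discharge, 30, and 90 days post-operation". Section 15.1 uses the baseline value for QALYs. QoR-15, PRO-diGI and the Barthel Index have no baseline measurement in Table 4.

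Section 14.2 describes itself as an outline, and section 14.2.4 leaves missing-data and sensitivity methods for secondary outcomes to the SAP.

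**The concern.** A score on the same instrument before randomisation is an obvious candidate to explain later variation. In a linear model, adjusting for it does not change what is estimated (the mean difference between arms). It removes explained variance and corrects chance imbalance in prior health. Section 14.2.2 fixes a covariate list without it. A SAP that follows the protocol literally would report wider EQ-5D-5L intervals than the data allow, and a SAP that adds the score would depart from the protocol's wording.

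A second, weaker matter concerns all the repeated scales. The copied model was written for one score at one time point, so it makes no stated use of discharge and day-30 scores when the day-90 form is not returned. Table 3 tracks this under "Return rate for 90-day questionnaire", with Red below 70%. If many forms were missing and the reasons differed by arm, a day-90 comparison of returned forms could mislead.

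**Working it through.** **The plan's own figure.** Section 14.1 gives "90% power, 5% two-sided significance threshold". It also says "we believe a 6 point reduction in CCI to be a feasible and relevant effect size" and "Previous literature has demonstrated the standard deviation of this measure to be ~27 for this population". Then n per arm = 2 × (1.960 + 1.2816)² × 27² / 6² = 425.5, rounded up to 426. Allowing 5% attrition, 426 / 0.95 = 448.4, rounded up to 449, or 898 in total. This matches the protocol. It concerns the CCI only. The protocol states no SD, correlation or power for any questionnaire, so everything below rests on assumed values, in SD units.

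**Precision from baseline EQ-5D-5L.** Let r be the correlation between baseline and follow-up that remains after the covariates already in the model. Adding baseline multiplies the variance of the arm difference by 1 − r² and the standard error by √(1 − r²). The equivalent gain in participants is 1/(1 − r²) − 1.

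| Assumed r | Variance ratio | SE ratio | SE reduction | Equivalent extra participants |
|---|---|---|---|---|
| 0.2 | 0.96 | 0.980 | 2% | 4% |
| 0.3 | 0.91 | 0.954 | 5% | 10% |
| 0.4 | 0.84 | 0.917 | 8% | 19% |
| 0.5 | 0.75 | 0.866 | 13% | 33% |

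For scale, at 70% return there are 0.7 × 449 = 314 per arm. The SE is then √(2/314) = 0.080 SD without baseline and 0.080 × 0.917 = 0.073 SD with it at r = 0.4. Participants without a recorded baseline contribute no gain, so the table is an upper figure if many cannot complete the form.

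**Gain from earlier scores where there is no baseline.** Assume correlation 0.6 between any two post-operative scores. Discharge and day-30 scores together explain R² = 2 × 0.36 / 1.6 = 0.45 of the day-90 score. With a proportion p returned, the variance ratio against returned forms alone is 0.45p + 0.55. This gives 0.865 at p = 0.7 (about 13% lower variance) and 0.955 at p = 0.9 (about 4 to 5% lower).

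**Bias at day 90.** Large-sample simulation used 1,000,000 records per scenario, 70% return overall, post-operative correlation 0.5 or 0.7 and baseline correlation 0.4. Return depended logistically on the day-30 score. True effects were none, 0.2 SD throughout, or 0.3, 0.2 and 0.1 SD at the three times.

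- Same return mechanism in both arms: the error of the day-90 regression on returned forms was about 0 with no effect, and at most about 0.02 SD, towards zero, with an effect.
- Dependence stronger in one arm (logistic slope 1.0 against 0.5): the error was about 0.05 to 0.09 SD, and it was present with no true effect (0.064 and 0.089 SD).
- Adding baseline alone in that second case left about 0.03 to 0.07 SD.
- Using baseline, discharge and day-30 scores left at most about 0.006 SD in any scenario.

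**The case against.** The strongest reply is that section 14 is an outline and the SAP will give the detail. That answers the missing-data question, which section 14.2.4 expressly defers. It does not answer the covariate point, because sections 14.2.1 and 14.2.2 do state the covariates and baseline EQ-5D-5L is not among them.

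It is also fair to say that recalled pre-illness health may predict recovery only modestly, and that some participants will have no baseline. At r = 0.2 the gain is only 2%. The change is nevertheless free, and a gain is expected at any non-zero correlation.

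A reader might go further and infer that the protocol commits to separate complete-case regressions that are biased at day 90. The text does not support this. It says neither 'separate' nor 'complete-case', although copying a single-time-point model suggests one fit per time. Return that depends on earlier scores is not enough for material bias; the dependence must differ by arm. In an unblinded trial that is plausible, but nothing in the protocol shows it. Nor does Table 3 simply accept 30% non-return: 70 to 99% is Amber and triggers a review of trial processes.

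A reader might also conclude that a repeated-measures model should replace the regression for every scale. That is a debatable trade. Such a model carries the earlier scores of people who die and so implicitly extrapolates beyond death, where section 1.1 cites 90-day mortality of 9.6%. It also treats discharge as a fixed visit, although the day-30 text in section 9 allows for participants not yet discharged. Finally, the baseline gain cannot be credited to QoR-15, PRO-diGI or Barthel, which have no baseline.

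**Conclusion.** The point holds for EQ-5D-5L: the stated covariate list omits a baseline score that is collected before randomisation. The cost is precision, about 2% to 13% of the standard error for assumed correlations of 0.2 to 0.5, less where baseline is often missing. Leaving the score out does not in itself bias the randomised comparison.

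The day-90 return issue supports an optional supporting analysis and nothing stronger. The 0.05 to 0.09 SD bias, against a standard error of about 0.08 SD, needs both heavy non-return and a mechanism that differs by arm. All correlations, return rates and mechanisms here are assumptions. Only secondary outcomes are affected; the primary analysis and the sample size of 898 stand.

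**What to change.** In section 14.2.2, add that the EQ-5D-5L analyses at discharge, 30 and 90 days include baseline EQ-5D-5L as a covariate, with a missing-value indicator or mean imputation for participants who could not complete it, so that nobody is dropped for lack of a baseline. Carry the same wording into the SAP.

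Optionally, name a supporting analysis for EQ-5D-5L, QoR-15, PRO-diGI and Barthel that uses earlier post-operative scores: a repeated-measures model or multiple imputation among survivors, with deaths reported separately. Adding baseline alone would not serve this purpose, since it left most of the simulated bias in place.

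The cost is protocol and SAP wording, with no new data. It is best settled before any statistician is unblinded.

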#### **14.2.3 Planned subgroup analyses**

Subgroup analyses will be performed on two variables used in the minimisation algorithm (NELA Risk ( $\geq 5\%$ ) and NRS  $\geq 4$  see Section 6 and performed on the primary outcome only. The effects of these subgroups will be examined by including an intervention group by subgroup interaction parameter in the regression model, which will be presented alongside the effect estimate and 95% confidence interval within subgroups. The results of subgroup analyses will be treated with caution and will be used for the purposes of hypothesis generation only.

#### **14.2.4 Missing data and sensitivity analyses**

Since CCI at hospital discharge can be obtained from the patient's medical history and notes, there should be minimal missing data for the primary outcome. The sample size

calculation has incorporated a potential 5% attrition rate to allow for up to 5% missing data in the primary outcome. If the level of missing data is greater than 5%, then additional sensitivity analyses will be performed to investigate the impact of missing data. Full details of missing data and sensitivity analysis, including on secondary outcomes will be included in the Statistical Analysis Plan.

### **14.3 Planned final analyses**

The primary analysis for the trial will occur once all participants have completed the final 90 day post-operative assessment and corresponding outcome data has been entered onto the EDC system and validated as being ready for analysis.

## 15. HEALTH ECONOMICS

A cost-effectiveness analysis using individual patient data will be undertaken from the NHS and personal social service perspective, with a 90-day timeframe. Secondary analyses will adopt a societal perspective and a lifetime horizon. All analyses will use QALYs, based on the EQ-5D-5L, as the measure of health outcome. Cost Effectiveness will be assessed probabilistically using the relevant funding thresholds recommended by NICE at the time of analysis. A value of information analysis will be undertaken using the results based on the lifetime horizon in order to identify the value of further research.

### 15.1 Within-trial economic evaluation

This will adopt recommended methods for economic evaluations that are undertaken alongside controlled trials. Resource use will cover length and type of hospital stay (as described by healthcare resource group); which will include adverse events (e.g. infections and further operations) but not details of PN. Days of PN will be recorded separately, for the purposes of the trial. After discharge, all other NHS and personal social service utilisation will be collected using a patient questionnaire, together with private expenditure and time off work for an analysis from a societal perspective. Unit costs will use mean national reference cost values, whilst the costs of PN will be based on a survey of consumable costs in the trial hospitals and estimates of staff time required for the initiation and cessation of PN. QALYs will be calculated based on EQ-5D-5L recorded at baseline, discharge, 30 days and 90 days. Utilities will be calculated using the method recommended by NICE at the time of analysis; whilst NICE currently recommends the use of a mapping approach, it is anticipated that an official tariff will be available in the near future. An incremental analysis will then be undertaken. A comprehensive one-way sensitivity analysis will be undertaken, together with a probabilistic sensitivity analysis with plots on the cost-effectiveness plane and the generation of cost-effectiveness curves and its associated frontier.

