### **Patient reported outcomes**

- Recovery using the Surgical Quality of Recovery-15 (QoR-15) on discharge, 30 and 90 days post-operation
- EuroQoL-5D-5L (EQ-5D-5L) on discharge, 30 and 90 days post-operation
- Gastrointestinal recovery (PRO-diGI) on discharge, 30 and 90 days post-operation
- Assessment of patient treatment satisfaction using a visual analogue scale 30 and 90 days post-operation

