### 7.2 Trial intervention: Parenteral Nutrition

The trial intervention is intentionally pragmatic. Patients randomised to the intervention arm will receive early PN which will be administered intravenously and should be delivered either through a dedicated lumen of a central line placed at operation, or through a PICC line. These lines are inserted by anaesthetists or by specialised vascular access services, depending on local service specifications. Line access may be secured at any point from randomisation to commencement of intervention. Placement of these lines will be confirmed with a plain radiograph of the chest and is undertaken as per local processes, using aseptic techniques. Blood tests are performed prior to commencement of PN to ensure sodium, potassium, magnesium, and phosphate are in the correct range

PN is available pre-formulated from multiple suppliers in the UK. The trial does not specify or mandate the use of any particular brand; participating sites should continue to use the PN formulation routinely employed in their standard clinical practice. Sites will already have familiarity with a particular brand and will use this for the trial. PN provides carbohydrates, lipids, amino acids, vitamins, trace elements, electrolytes and water. These amounts vary according to the supplied bag. An appropriate base PN bag is selected based upon the nutrients required, particularly calories. Additional electrolytes can be added, tailored to the patient's biochemistry. The administration of PN is defined in UK guidance from NICE[26], which provides guidance on calculating calorie requirements. Sites will calculate appropriate rates of PN to be administered prior to commencement. Out of hours, this may include administering a volume defined by local out-of-hours feeding protocols, rather than a dose tailored to exact calorie requirements. At the commencement of PN, dosing is at a reduced rate to avoid metabolic consequences. This is slowly increased with ongoing monitoring of blood tests for evidence of electrolyte disturbance (e.g. abnormal sodium, potassium, phosphate, or magnesium levels). Blood tests (biochemistry including renal and liver function) are required daily for the first week of administration and

---

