### **Day 30 post-operation**

The participant will be contacted by the research team. Complications will be captured from medical records, and from telephone discussion with the participant to identify those complications managed in the community. This includes unplanned readmissions if the patient has been discharged post-operation. Patient reported outcomes of PRO-diGI, QoR-15, EQ-5D-5L, and patient treatment satisfaction will be collected using an adaptive approach of telephone or electronic administration. Barthel Index will be completed by a member of the research team. These assessments should take place at day 30 +/- 3 days post-operation.

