## **Day 90 post-operation**

Complications will be captured from medical records, and from telephone discussion with the participant to identify complications managed in the community. This includes unplanned readmissions following discharge. Patient reported outcomes of PRO-diGI, QoR-15, and patient treatment satisfaction will be collected using an adaptive approach of telephone or electronic administration. Barthel Index will be completed by a member of the research team. These assessments should take place at day 90 +/- 7 days post-operation.

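### The economic evaluation omits recurring PN monitoring from the PN cost, takes its only pre-discharge utility from before the illness, and loses EQ-5D-5L in the day-90 visit text

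*Protocol*

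**What the plan says.** **PN cost.** Section 15.1 describes hospital resource use by length and type of stay (healthcare resource group), and states that this leaves out PN detail. PN days are recorded separately. PN itself is costed from a survey of consumables in the trial hospitals and "estimates of staff time required for the initiation and cessation of PN". Section 7.2 says: "Blood tests (biochemistry including renal and liver function) are required daily for the first week of administration". Testing then stays daily until results are stable. The PN column of Table 2 repeats daily electrolyte monitoring for seven days and adds liver-function and line-sepsis monitoring.

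**Utilities.** Section 15.1: "QALYs will be calculated based on EQ-5D-5L recorded at baseline, discharge, 30 days and 90 days". The baseline paragraph of Section 9 has participants answer "based on their health and wellbeing prior to the start of the episode that requires surgery", and adds: "If the participant is not able to complete this then EQ-5D-5L will not be recorded". Table 4 shows no other EQ-5D-5L before discharge.

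**Day 90.** The Section 9 day-30 text reads: "Patient reported outcomes of PRO-diGI, QoR-15, EQ-5D-5L, and patient treatment satisfaction will be collected". The matching day-90 sentence reads: "Patient reported outcomes of PRO-diGI, QoR-15, and patient treatment satisfaction will be collected using an adaptive approach of telephone or electronic administration". The trial summary lists "EuroQoL-5D-5L (EQ-5D-5L) on discharge, 30 and 90 days post-operation". Table 3, Section 8.2.2.1, Table 4 and Section 15.1 also need the day-90 value.

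**The concern.** Section 15.1 itself fixes the PN cost components and the QALY time points, and Section 15 refers to no separate health-economics plan.

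On cost, the intervention brings recurring work on each PN day: blood tests, review and prescribing. The listed components cover materials and the start and end of PN. If the recurring work is costed nowhere, the gap falls mainly on the early-PN arm and favours it.

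On QALYs, someone about to have an emergency laparotomy is not in their pre-illness state. If the pre-episode score is the first point of the utility curve, the inpatient segment runs from usual health down to discharge health and the acute trough never appears. That segment's length is the hospital stay, which is a secondary outcome and may differ between arms.

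On day 90, sites working from the visit text could leave out the questionnaire that closes the last segment of the curve.

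**Working it through.** Section 15 gives no utility, unit cost or QALY figure, so there is no economic figure to reproduce. Every value below that is not a protocol time point or monitoring period is an assumption.

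**1. PN cost: requirement against cost component**

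- Materials: covered by the consumables survey.
- Staff time to start and stop PN: covered. Line insertion and the confirming chest X-ray may fall here.
- Daily bloods in week one and until stable, with daily nutrition-team review: no listed component. The stay cost is by healthcare resource group and leaves out PN detail.

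Assume £25 to £60 per day for tests and staff time, over the seven days in Section 7.2:

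- 7 × £25 = £175 and 7 × £60 = £420 per PN participant.
- At an assumed £20,000 per QALY: 175/20,000 = 0.009 and 420/20,000 = 0.021 QALY.

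This treats every monitored day as extra to usual care, so for seven days it is a ceiling. PN stopped earlier lowers it; longer PN with unstable results raises it.

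**2. Starting utility**

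The protocol names no formula. The conventional area under the curve, with stay of L days, is

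QALY = [L(u0 + uD)/2 + (30 − L)(uD + u30)/2 + 60(u30 + u90)/2] / 365.

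Assume uD = 0.50, u30 = 0.65, u90 = 0.75, L = 12 and a pre-illness utility of 0.85. The last two segments contribute 18 × 0.575 = 10.35 and 60 × 0.70 = 42. The change per extra night is (u0 − u30)/730.

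| Starting value u0 | QALY | Change per extra night |
|---|---|---|
| 0.85 (pre-illness) | (8.10 + 10.35 + 42)/365 = 0.1656 | +0.0003 |
| 0.50 (discharge value carried back) | (6.00 + 10.35 + 42)/365 = 0.1599 | −0.0002 |
| 0.30 (acute) | (4.80 + 10.35 + 42)/365 = 0.1566 | −0.0005 |
| 0 (acute) | (3.00 + 10.35 + 42)/365 = 0.1516 | −0.0009 |

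- Overstatement per participant, both arms: L(0.85 − u0)/730 = 0.006 to 0.014 QALY.
- Between-arm error per night of difference in stay: (0.85 − u0)/730, that is 0.35/730 = 0.0005, 0.55/730 = 0.0008 and 0.85/730 = 0.0012 QALY. At £20,000 per QALY this is about £10 to £23.

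A wider range takes a pre-illness minus acute gap of 0.3 to 0.8. For stays of 7 to 21 days the overstatement is 0.003 to 0.023 QALY in both arms. For a 1 to 3 day difference in stay the between-arm error is 0.0004 to 0.0033 QALY.

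**3. Day 90**

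The day-30 and day-90 sentences are parallel except that EQ-5D-5L is missing from the second. Five other places require it. Days 30 to 90 make up 60/90 = 67% of the horizon.

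**The case against.** **Cost.** The scope of the consumables survey is undefined, and resource-group costs already carry average ward bloods in both arms. Control patients after emergency laparotomy also have bloods taken and may receive PN from day five. The daily dose adjustment in Table 2 is a permission, not a required cost. All of this stands, and it means £175 to £420 is not an incremental cost. It does not close the gap: the staff-time wording is limited to initiation and cessation, and a resource-group average does not pick up additional PN-day work. A reader might divide the omitted cost by a small QALY gain and infer a large shift in cost per QALY. The documents give neither a unit cost nor an expected gain, so no such figure is supported.

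**Starting utility.** Section 15.1 does not place the baseline score at day 0. It commits to recommended methods and a comprehensive one-way sensitivity analysis. That stands: the day-0 placement is inferred from there being no other pre-discharge value. Randomisation also balances the level shift in expectation, leaving mainly the length-of-stay term. A reader might infer that the QALY comparison is reversed. The sign change above concerns only the per-night term. It requires pre-illness utility to exceed day-30 utility and discharge utility not to depend on stay, and the quantity is small. A reader might also infer that the sickest participants drop out of the QALY analysis because their baseline is not recorded. Section 14.2.4 leaves missing-data handling to the statistical analysis plan, so that is not shown.

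**Day 90.** A reader might infer that EQ-5D-5L is not collected at day 90. The schedule and four other places say it is, and Table 3 makes the 90-day return rate a pilot criterion, so a systematic loss should be noticed. This is a slip in the visit text.

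**Conclusion.** The point holds in three parts of unequal weight; none touches the primary clinical analysis.

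1. The PN costing rule leaves out a recurring cost that the protocol's own monitoring requirements create. The incremental cost of early PN is likely understated. The documents do not fix the amount; the figure above is a seven-day ceiling under assumed unit costs, and the net figure will be lower. This part matters most, because its direction is clear and favours PN.
2. A pre-episode score is a QALY time point with no acute-state value beside it. Under a conventional area-under-the-curve calculation this inflates inpatient QALYs in both arms. The between-arm error is roughly 0.001 QALY per night of difference in stay, towards the longer-stay arm. It rests on assumed utilities.
3. The day-90 visit text contradicts the schedule and should be reconciled with it. No assessment is missing from the plan.

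**What to change.** - **Section 15.1, cost:** add per-day monitoring tests and nutrition-team time, multiplied by recorded PN days, in both arms. State whether line insertion and chest X-ray count as initiation, so that they are costed once. PN duration is already recorded for each arm; the extra work is unit costs and a staff-time estimate. The PN cost will become somewhat less favourable.
- **Section 15.1, QALYs:** use the pre-episode EQ-5D-5L as a regression covariate. Start the curve from one stated acute utility common to both arms, which is reasonable because randomisation is pre-operative. Vary that value in sensitivity analysis, including carrying the discharge score back. The starting value is unmeasured, so it should be presented as a convention. This needs wording only.
- **Section 9, day 90:** add EQ-5D-5L to the list of patient-reported outcomes. This is a one-line correction with no new data collection.
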